6.1.2 Treatment duration

The duration of treatment with eltrombopag will be based on the reasons described below and other reasons for early withdrawal ([Section 7.2.3.17.2.3.1](#)):

- If no partial or complete hematological response is observed at 16 weeks and maintained afterwards, the patient will be withdrawn from the study.
- In patients achieving complete response without transfusion support for a minimum of 8 weeks, the dose of eltrombopag may be reduced by 50%, and discontinued if counts remain stable after 8 weeks at the reduced dose. If relapse occurs after eltrombopag discontinuation, eltrombopag can be reintroduced at the last effective dosage.
- If new clonal cytogenetic abnormalities associated with dysplastic bone marrow findings are observed such as monosomy 7, eltrombopag should be permanently discontinued.

- If the patient develops myelodysplastic syndrome (MDS) or acute myeloid leukemia (AML) assessed by sensitive methods, eltrombopag will be permanently discontinued.
- If other non-clonal and/or cytogenetic abnormalities with uncertain meaning not previously observed and not associated with worsening blood counts or bone marrow dysplastic, the decision of discontinuing eltrombopag is up to the investigator, based on a more frequent bone marrow aspirate monitoring of cytogenetic abnormalities and dysplastic findings.
- If relapse of previous hematological disease occurs, eltrombopag will be permanently discontinued.
- If patient receives a new HSCT, eltrombopag will be permanently discontinued

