7.1 Study flow and visits schedule

Table 7-1 lists all of the assessments and indicates with an “X”, the visits when they are performed. All data obtained from these assessments must be supported in the patient’s source documentation.

Tests, procedures, and visits that occur within the planned allowable windows as specified below will not constitute protocol deviations. All visit intervals are calculated from the first dose of eltrombopag that will take place on Day 1. All attempts should be made to return to the original schedule of visits if visits are completed out of window. Weekly and biweekly visits should be completed \pm 1 day. Monthly visits and every 6-week visits should be completed \pm 3 days. Bone marrow testing may be performed \pm 1 month from the scheduled time point except in the screening visit where BMA must be done in the screening period (within 28 days).

Table 7-1 Visit evaluation schedule

	Protocol Section	Screening/ baseline	Day 1	Weekly visits (±1 day)				Visits every 2 weeks (±1 day)				Monthly visits (± 3 days)				Approx. every 6 weeks (±3 days) up to 36 weeks		Final Visit (or Early Withdrawal) *
				W 1	W 2	W 3	W 4	W 6	W 8	W 10	W 12	W 16	W 20	W 24	W 30	W 36	W 40	
				1	2	3	4	5	6	7	8	9	10	11	12	13	14	15
Visit Number	Day of visit	-28 to day 0	-7 to day 0	Day 1	Day 8	Day 15	Day 22	Day 29	Day 43	Day 57	Day 71	Day 85	Day 113	Day 141	Day 169	Day 211	Day 253	Day 283
Pregnancy test ^d	7.3.2.6		X						X		X		X	X	X	X	X	X
ECG	7.3.2.7	X													X			X
Ophthalmological examination	7.3.2.8	X													X			X
Blood smear ^e	7.3.2.5		X						X		X		X	X	X	X	X	X
Dispense/collect eltrombopag ^g	6.5			X	X	X	X	X	X	X	X	X	X	X	X	X	X ^h	
Concomitant Medication inquiry	6.3	Record from signing of Informed Consent Form																
Adverse events inquiry	8.1	Record from signing of Informed Consent Form																
Hematological response	7.3.1.1												X	X	X	X	X	X
Survival status	7.2.4													X		X	X	

^a A post-transplant local conventional cytogenetics or FISH will be allowed if has been done as per clinical practice within 8 weeks prior to Day 1. If not available, a conventional cytogenetic or FISH (if conventional cytogenetics does not show metaphase) has to be locally performed at Screening within 28 days prior to Day 1.

^b Height will only be assessed at baseline.

^c Hematology biochemistry and other analysis do not need to be repeated at Day 1 as they should have been performed within 7 days prior to the start of treatment.

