^d Women of childbearing potential must undergo a serum pregnancy test at screening to confirm eligibility in the study. Subsequently, women of childbearing potential must undergo a pregnancy test (urine or serum) at the specified visits.

^e Blood smears must also be performed any time if considered necessary.

^g In patients who discontinue eltrombopag because efficacy according to Section 6.1.2, medication will not be dispensed; if a loss of response occurs, eltrombopag can be reintroduced at the last effective dose.

^h In responder patients, continuation of eltrombopag should be up to the investigator. After the 36 weeks of the study, the suitability of continuing eltrombopag in a commercial setting will be evaluated by the investigator.

* Patients who prematurely withdraw from the study should return and complete the assessments associated with Week 40 visit 30 days after the last dose of eltrombopag.

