7.2.3 Final visit (or Early withdrawal)

For patients who complete the 36-weeks of study treatment administration and/or assessments, or permanently stop taking study treatment for any reason, this visit should be performed 30 days after the last dose of eltrombopag:

- Supportive care (see [Section 6.3.1.1 / 7.3.1.2](#))
- Physical examination (See [Section 7.3.2.1](#)).
- Karnofsky performance status (See [Section 7.3.2.2](#))
- Weight (See [Section 7.3.2.3](#))
- Vital signs (See [Section 7.3.2.4](#))
- Hematology biochemistry and other analysis (See [Section 7.3.2.5](#))
- Urine or serum pregnancy test should be performed in women of childbearing potential (See [Section 7.3.2.6](#)).
- Blood smear (See [Section 7.3.2.5](#))
- ECG (See [Section 7.3.2.7](#))
- Ophthalmological monitoring (see [Section 7.3.2.8](#))
- Record any concomitant medication (See [Section 6.3](#))
- Record adverse events (See [Section 8.1](#)). If required (per investigator's opinion), another visit could be scheduled to follow up properly the patient's AE/SAE. This will be considered as an unscheduled visit, and the assessments to be made will be at the discretion of the investigator. Results will become part of the patient's medical history.

Patients lost to follow-up should be recorded as such on the CRF. For patients who are lost to follow-up, the investigator should show "due diligence" by documenting in the source documents steps taken to contact the patient, e.g., dates of telephone calls, registered letters, etc. At a minimum, all patients who discontinue treatment, including those who refuse to return for a final visit, will be contacted by phone for safety assessment during the 30 days following the last dose of study treatment.

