10.5.1 Other efficacy objective(s)

- To determine the response in each haematological lineage separately, the absolute frequency and valid percentage of patients who have a response in the neutrophil, platelet, and Hb lineages separately after 16, 24 and 36 weeks of eltrombopag, will be presented with the 95% CI. Descriptive statistics will also be provided between baseline and weeks 16, 24 and 36 for ANC, platelets and hemoglobin levels, and the appropriate paired exploratory tests will be done according to the type of distribution (parametric or not) to assess the statistical significance of the changes.
- To evaluate the overall hematological response rate (partial and complete) at 24 and 36 weeks after the initiation of eltrombopag, the frequency and percentage distribution and the corresponding 95% CI will be provided. This CI will be constructed as for the primary efficacy endpoint. Descriptive statistics will also be provided between baseline and week 24 and week 36 for ANC, platelets count and hemoglobin levels, and the appropriate paired exploratory tests will be done according to the type of distribution (parametric or not) to assess the statistical significance of the changes.
- To evaluate transfusion independence, the percentage of patients who were previously transfusion-dependent and do no longer require a RBC or platelet transfusion before and after the first 16 weeks of treatment will be calculated along with the 95% CI. This CI will be constructed as for the primary efficacy endpoint. The period where patients did not receive any platelet or RBC transfusions during the treatment period and follow-up will also be analyzed.

- To evaluate the discontinuation or reduction of concomitant G-CSF and/or EPO therapy, the percentage of patients who discontinue or reduce by $\geq 50\%$ from baseline the use of concomitant G-CSF and/or EPO therapy will be calculated along with the 95% CI. This CI will be constructed as for the primary efficacy endpoint.
- Overall survival, defined as the duration from inclusion in the study to date of death (whatever the cause), will be estimated with the Kaplan-Meier curves method and two-sided 95% CI for the estimated median. All patients who discontinue from the study, regardless the reason of discontinuation, will be followed for survival for 24 and 36 weeks, unless they withdraw their consent, die or are lost-to follow-up, in which case will be censored at the last contact.

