## 2.2 Study Design

This study is designed as an open-label, single-arm phase II study, in which patients diagnosed with primary or secondary PGF after allo-HSCT will be treated with eltrombopag up to week 36 or until the patient's premature withdrawal. If patient terminates eltrombopag for any of the reasons established in the withdrawal criteria, he/she will be followed for safety up to 30 days after the last dose of eltrombopag, unless he/she withdraws the consent, dies or is lost-to follow-up.

The primary efficacy endpoint is the overall hematologic response rate (partial and complete) by 16 weeks after the initiation of eltrombopag. Eltrombopag will be initiated on day 1 at a dose of 150 mg once daily (75 mg daily in Asian ancestry patients) and will be continued up to 36 weeks.

The study will consist of the following periods:

- Screening Period (baseline): the patient will be invited to participate in the study, after being informed of its characteristics. The patient screening criteria will then be reviewed, and the procedures established in the evaluation schedule will be performed.
- Treatment Period: from administration of the first dose of eltrombopag until time when patient permanently stops taking study treatment for any reason or until 36 weeks have passed.
  - Only patients with a partial or complete response at week 16 will continue to receive eltrombopag until loss of response (defined as a decrease in blood counts to levels that do not continue to meet the criteria for response established in this protocol), unacceptable toxicity, or discontinuation for any other reason.
  - Patients who discontinue eltrombopag because efficacy, will continue in the study and attend the scheduled visits of Treatment Period as per protocol. If loss of response occurs, eltrombopag will be reintroduced at the last effective dose.
- During the Treatment Period, patients will be evaluated weekly during the first month, every 2 weeks during the next 2 months and subsequently every 4 weeks until week 24. For the last 3 months, patients will be followed every 6 weeks.
- Final Visit (or Early Withdrawal): this visit will take place 30 days after completion of the Treatment Period, or premature patient withdrawal.

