**8 TREATMENT**

- Patients with 16 weeks of treatment who discontinue due to no response
- Patients with treatment in week 36.
- Patients with at least one dose modification (No /Yes). For each dose modification, it will be shown the reasons.
- Duration of treatment (days, from the start date to the end date). If the patient has modified the dose, it will be shown the duration for each dose indicated.

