**To evaluate the transfusion independence for red blood cells (RBC) and/or platelets after the initiation of eltrombopag.**

It will be calculated:

- The patient receive at least one transfusion before start treatment (No / Yes) (data in section “Supportive Care Record”).
- The patient receive at least one transfusion after start treatment and before week 16 (No / Yes) (data in section “Supportive Care Record”).
- The patient receive at least one transfusion after week 16 and before end treatment (No / Yes) (data in section “Supportive Care Record”).

In each of the studied moments, it will be shown the number of transfusions per patient. In addition, for total of transfusions, it will be shown the type of transfusion (Platelets / RBC).

It will be performed:

- Analysis of contingency tables between number of patients with transfusions before start treatment and before week 16, using chi-square or Fisher's exact test.
- Analysis of contingency tables between number of patients with transfusions before start treatment and after week 16, using chi-square or Fisher's exact test.

It will be calculated:

- The period of time where patients did not receive any platelet or RBC transfusions during the treatment period, calculated as the difference between the number of days in treatment and the number of days with transfusions.

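### SAP 10.4 drops the follow-up that protocol 10.5.1 includes in the transfusion-free period, and its day count reflects treatment length more than transfusion independence

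*SAP*

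**What the plan says.** Protocol Table 3-1 lists, under transfusion independence, the time during which a patient has no platelet or RBC transfusion. It gives neither a window nor a formula. Protocol 10.5.1 supplies the window: "The period where patients did not receive any platelet or RBC transfusions during the treatment period and follow-up will also be analyzed".

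SAP 10.4 (Secondary objective 3) restricts the variable to the treatment period and gives the formula: "calculated as the difference between the number of days in treatment and the number of days with transfusions". Its last yes/no transfusion item also closes at the end of treatment.

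Transfusion data are collected beyond that point. Protocol 7.2.3 lists supportive care among the Final Visit assessments and states that "this visit should be performed 30 days after the last dose of eltrombopag". A footnote to protocol Table 7-1 has patients who withdraw early "return and complete the assessments associated with Week 40 visit 30 days after the last dose of eltrombopag".

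Treatment length differs between patients by design. Protocol 6.1.2 states: "If no partial or complete hematological response is observed at 16 weeks and maintained afterwards, the patient will be withdrawn from the study". Others may be treated to week 36. For those who stop because the drug has worked, SAP 2.2 states: "Patients who discontinue eltrombopag because efficacy, will continue in the study and attend the scheduled visits of Treatment Period as per protocol". SAP 10.4 does not say what counts as a day in treatment.

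**The concern.** There are two separate issues.

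The first is the window. The protocol promises an analysis that extends past treatment, and the SAP stops at the end of treatment. Protocol 6.2.3 says that platelet counts go back to baseline within 2 weeks of stopping eltrombopag in most patients. The weeks after the last dose are therefore informative about whether independence lasts.

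The second is the measure. Each transfusion day removes one day from the total, and every day between transfusions counts as free. A patient transfused on a regular schedule can therefore accumulate a large value, and a longer course of treatment raises it further.

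This is the only duration reported for secondary objective 3. A reader of the study report could take a long value as evidence of long-lasting independence when it is not.

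**Working it through.** The plan states no figure for this variable, so there is none to reproduce. The check applies the SAP formula to constructed patients.

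**Inputs from the documents**
- Timing: "All visit intervals are calculated from the first dose of eltrombopag that will take place on Day 1" (protocol 7.1). Table 7-1 puts week 16 at Day 113, week 36 at Day 253 and the Final Visit at Day 283.
- Treatment length: 16 weeks = 112 days for a patient who leaves at week 16; 36 weeks = 252 days at most.
- Final Visit: 30 days after the last dose.

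**Assumptions**
- Follow-up in protocol 10.5.1 means the time to the Final Visit.
- Transfusion frequency is not given, so 1, 2 or 3 evenly spaced transfusion days a week are shown.

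**Step 1: days left out**
- Week-36 patient: 283 − 253 = 30 days; 30 / (252 + 30) = 30/282 = 10.6%.
- Week-16 patient: 30 / (112 + 30) = 30/142 = 21.1%.

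**Step 2: same total, different patterns**

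Take 112 days of treatment with 16 transfusion days. The SAP value is 112 − 16 = 96 in both cases below.
- All 16 at the start (Days 1 to 16): longest free run is Days 17 to 112, or 96 days.
- One a week throughout: longest free run is 6 days.

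**Step 3: regular transfusion throughout**

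| Transfusion days per week | SAP value, 112 days | SAP value, 252 days | Share free | Longest free run |
|---|---|---|---|---|
| 1 | 112 − 16 = 96 | 252 − 36 = 216 | 86% | 6 days |
| 2 | 112 − 32 = 80 | 252 − 72 = 180 | 71% | 3 days |
| 3 | 112 − 48 = 64 | 252 − 108 = 144 | 57% | 2 days |

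Within each row the share free and the longest run are the same at both lengths. The total rises by 252/112 = 2.25 times only because treatment is longer.

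**Step 4: treatment length against transfusion effect**
- At one transfusion day a week, going from 16 to 36 weeks of treatment adds 216 − 96 = 120 days.
- Removing every weekly transfusion adds 112 − 96 = 16 days over 16 weeks, or 252 − 216 = 36 days over 36 weeks.

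**Step 5: can a regularly transfused patient stay to week 36?**

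Yes. Under protocol 7.3.1.1 a partial response needs any one of three criteria. The neutrophil criterion applies when pretreatment ANC was below 1,000/µL and carries no transfusion condition. How many such patients there would be cannot be known from the documents.

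**The case against.** The strongest reply has four parts.

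- **The window.** Table 3-1 sets no window, so the SAP departs from protocol 10.5.1 but not from the endpoint definition. Follow-up is not defined for transfusions. The protocol lists the Final Visit separately from follow-up for survival, and describes the latter in terms of survival only. This stands as a limit on the size: the 30 days are one reading. The mismatch itself remains, because 10.5.1 names a period beyond treatment and SAP 10.4 does not.
- **The formula.** Subtracting transfusion days from treatment days is a literal way to count time without transfusion. This stands too. A reader might infer that the SAP contradicts a protocol requirement for continuous independence, but neither Table 3-1 nor 10.5.1 says continuous. The measure falls short of the objective; it does not breach the text.
- **The illustrations.** The transfusion rates are assumed. Treatment length also carries some information, since non-responders leave at week 16. Both points are fair. Step 2 holds treatment length fixed, so its result does not depend on comparing long and short courses.
- **Other outputs.** SAP 10.4 gives yes/no tables and transfusion counts by period. SAP 10.2 gives lineage responses at weeks 16 to 36, where platelet response and hemoglobin partial response require transfusion independence. These compensate in part, but none gives a duration.

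A reader might also infer that patients who stop because of efficacy lose their off-drug days and so score below patients who are still being transfused. That needs days in treatment to mean days on drug, as the start-to-end-date duration in SAP 8 could suggest. SAP 2.2 points the other way, since these patients attend Treatment Period visits. The documents do not support a ranking claim; the term needs one clarifying sentence.

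**Conclusion.** The point holds as two findings of different weight.

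- **Conflict.** SAP 10.4 omits the follow-up that protocol 10.5.1 includes. If follow-up runs to the Final Visit, the loss is 11% of observed days for a full-course patient and 21% for a patient leaving at week 16.
- **Improvement, not contradiction.** The SAP total depends mainly on treatment length and cannot separate sustained independence from regular transfusion. The same value of 96 can go with a longest free run of 96 days or of 6. The transfusion patterns are assumed.

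It would go too far to treat the omitted 30 days as off-drug time for everyone. Protocol 4.1 and a Table 7-1 footnote allow the investigator to consider commercial eltrombopag after week 36, so some patients may be on drug then.

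The consequence is contained. The variable is secondary, descriptive and untested, and the primary analysis and sample size are unaffected. It is still worth correcting before analysis, because it is the only duration reported for its objective.

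**What to change.** Replace the last item of SAP 10.4 with a paragraph that does the following.

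- **Window.** Count from Day 1 to the last visit at which supportive care is recorded, ending at death or study exit. Include the Final Visit and the off-drug scheduled visits after an efficacy stop. State in one sentence that those off-drug visits count, and say what follow-up means for this variable.
- **Measure.** Report the longest continuous transfusion-free interval for platelets, for RBC and for either product, beside days observed.
- **If the day count is kept.** Give it as a proportion of days observed, with transfusions per 4 weeks. These remove the effect of treatment length but not of pattern: both patients in Step 2 have 96/112 = 86% free and, at one transfusion per transfusion day, 16/112 × 28 = 4 transfusions per 4 weeks. The longest interval is what separates them.
- **Periods.** Show the period to the end of study treatment and the period from then to the Final Visit, separately and combined. Flag patients who continue commercial eltrombopag after week 36, so that the second period is not labelled off-drug for them.

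The cost is one SAP paragraph and a little more programming. No new data are needed. Protocol 7.3.1.2 has transfusions monitored at each visit, protocol 6.3 requires them to be listed on the Concomitant Medications CRF, and the SAP's own formula already presupposes transfusion dates. SAP 10.5 already uses the Supportive Care Record up to visit 16, the week 40 Final Visit, for G-CSF and EPO.

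The downside is that reported durations will look less favourable. The longest interval also still grows with observation time, so it has to be read with days observed.

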#### **10.5 Secondary objective 4**

##### **To evaluate the reduction and discontinuation of concomitant granulocyte colony-stimulating factor (G-CSF) and/or erythropoietin (EPO) therapy.**

It will be calculated:

- The patient receive EPO at start of treatment (No / Yes) (data in section "Supportive Care Record").
- The patient receive EPO in visit 6, visit 9, visit 11, visit 13, visit 15 and visit 16 (No / Yes) (data in section "Supportive Care Record").
- The patient reduce EPO at least 50% from start of treatment to visit 6, visit 9, visit 11, visit 13, visit 15 and visit 16 (No/ Yes) (data in section "Supportive Care Record").
- The patient receive G-CSF at start of treatment (No / Yes) (data in section "Supportive Care Record").
- The patient receive G-CSF in visit 6, visit 9, visit 11, visit 13, visit 15 and visit 16 (No / Yes) (data in section "Supportive Care Record").
- The patient reduce G-CSF at least 50% from start of treatment to visit 6, visit 9, visit 11, visit 13, visit 15 and visit 16 (No / Yes) (data in section "Supportive Care Record").

It will be realized:

- Analysis of contingency tables between number of patients who receive EPO at start of treatment and in visit 6, visit 9, visit 11, visit 13, visit 15 and visit 16, using chi-square or Fisher's exact test.
- Analysis of contingency tables between number of patients who receive G-CSF at start of treatment and in visit 6, visit 9, visit 11, visit 13, visit 15 and visit 16, using chi-square or Fisher's exact test.

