4.1 Description of study design

This study is designed as an open-label, single-arm phase II study, in which patients diagnosed with primary or secondary PGF after allo-HSCT will be treated with eltrombopag up to week 36 or until the patient's premature withdrawal. If patient terminates eltrombopag for any of the reasons established in the withdrawal criteria (see [Sections 6.1.2/7.2.3.1](#)), he/she will be followed for safety up to 30 days after the last dose of eltrombopag (Final Visit [or Early Withdrawal]), unless he/she withdraws the consent, dies or is lost-to follow-up.

The primary efficacy endpoint is the overall hematologic response rate (partial and complete) by 16 weeks after the initiation of eltrombopag. Eltrombopag will be initiated on day 1 at a dose of 150 mg once daily (75 mg daily in Asian ancestry patients) and will be continued up to 36 weeks.

The study will consist of the following periods:

- Screening Period (baseline): the patient will be invited to participate in the study, after being informed of its characteristics. The patient screening criteria will then be reviewed, and the procedures established in the evaluation schedule will be performed.
- Treatment Period: from administration of the first dose of eltrombopag until time when patient permanently stops taking study treatment for any reason (see [Sections 6.1.2/7.2.3.1](#)), or until 36 weeks have passed.
 - Only patients with a partial or complete response at week 16 will continue to receive eltrombopag until loss of response (defined as a decrease in blood counts to levels that do not continue to meet the criteria for response established in this protocol), unacceptable toxicity, or discontinuation for any other reason ([Sections 6.1.2/7.2.3.1](#))
 - Patients who discontinue eltrombopag because efficacy (See [Section 6.1.2](#)), will continue in the study and attend the scheduled visits of Treatment Period as per protocol. If loss of response occurs, eltrombopag will be reintroduced at the last effective dose (See [Section 6.1.2](#))

During the Treatment Period, patients will be evaluated weekly during the first month, every 2 weeks during the next 2 months and subsequently every 4 weeks until week 24. For the last 3 months, patients will be followed every 6 weeks.

- Final Visit (or Early Withdrawal): this visit will take place 30 days after completion of the Treatment Period, or premature patient withdrawal.

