7.2.4 Follow-up for survival

All patients who discontinue from the study, regardless the reason of discontinuation, will be followed for survival for 24 and 36 weeks, unless they withdraw their consent, die or are lost-to follow-up, in which case will be censored at the last contact/follow-up.

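### SAP 10.5 analyses G-CSF and EPO use at visit 16 as one time point, but visit 16 pools week-40 completers with early withdrawals seen at about week 20 or at another week

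*SAP*

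**What the plan says.** SAP 10.5 (secondary objective 4) uses six visits after the start of treatment. For G-CSF, current use is "The patient receive G-CSF in visit 6, visit 9, visit 11, visit 13, visit 15 and visit 16 (No / Yes"), and EPO has the same list. The same visits serve for a yes/no item on reduction of at least 50% from start of treatment, and for tests: "Analysis of contingency tables between number of patients who receive G-CSF at start of treatment and in visit 6, visit 9, visit 11", continuing through visits 13, 15 and 16, by chi-square or Fisher's exact test.

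Protocol Figure 4-1 gives these visits as weeks 4, 10, 16, 24, 36 and 40. Its column for visit 16 is headed as the final or early-withdrawal visit. Three places in the protocol set the timing of that visit:

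- Section 4.1: "this visit will take place 30 days after completion of the Treatment Period, or premature patient withdrawal".
- Section 7.2.3, which also lists supportive care among the assessments: "this visit should be performed 30 days after the last dose of eltrombopag".
- Table 7-1 footnote: "Patients who prematurely withdraw from the study should return and complete the assessments associated with Week 40 visit 30 days after the last dose".

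Early withdrawal is part of the design. Section 6.1.2 states: "If no partial or complete hematological response is observed at 16 weeks and maintained afterwards, the patient will be withdrawn from the study". After the final visit, Section 7.2.4 provides only that patients who discontinue "will be followed for survival for 24 and 36 weeks".

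Protocol 10.5.1 defines the endpoint as the percentage who discontinue, or reduce by at least 50% from baseline, and names no visit. The SAP has no visit windows, no split of visit 16 and no rule for withdrawn patients.

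**The concern.** The list in SAP 10.5 reads as a time course from week 4 to week 40. Two different things disturb it after week 16.

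- **Selection at visits 13 and 15.** The timing is right, but patients without a response at week 16 have left. Those who attend are essentially week-16 responders still on study, including any who stopped eltrombopag because of efficacy.
- **Mixed timing at visit 16.** Withdrawn patients come back into the series under this label, at whatever week they left plus 30 days. They are pooled with completers at week 40.

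A reader who follows the visit percentages could take a change in who attends for a change in growth-factor use. What is at stake is the interpretation of one secondary objective. Visits 6, 9 and 11 come before response-based withdrawal and are not affected by it.

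**Working it through.** **1. Timing.** Table 7-1 uses nominal day = 7 × week + 1. The plan's own figure reproduces: week 36 is Day 253, and 253 + 30 = 283, the day shown for the final visit.

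For a non-responder whose last dose is at the week-16 visit:

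- Week 16 = 7 × 16 + 1 = Day 113.
- Visit 16 = 113 + 30 = Day 143; (143 − 1)/7 = week 20.3. With the ±3-day window on the week-16 visit, this is Day 140 to 146, weeks 19.9 to 20.7.
- Gap to the nominal day: 283 − 143 = 140 days.
- Visit 13 is Day 169, so this patient's visit 16 falls 169 − 143 = 26 days before it.

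**2. Share of visit-16 records that come early.** Protocol 10.7 plans 33 patients and assumes 45% response: 0.45 × 33 = 14.85, about 15 responders and 18 non-responders. If nobody else leaves and all attend, 18/33 = 55% of records are from about week 20 and 15/33 = 45% from week 40. With 10 responders the early share is 23/33 = 70%. With 24 it is 9/33 = 27%.

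**3. Effect on current-use percentages.** The documents give no use rates, so the rates below are assumptions. Take 15 responders and 18 non-responders, and suppose that no patient ever changes G-CSF use.

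| Assumed users (responders + non-responders) | Start and visit 11 | Visits 13 and 15, valid % | Visits 13 and 15, total % | Visit 16 |
|---|---|---|---|---|
| 3 + 4 (about 20% in each) | 7/33 = 21.2% | 3/15 = 20.0% | 3/33 = 9.1% | 21.2% |
| 3 + 7 (20% and about 40%) | 10/33 = 30.3% | 20.0% | 9.1% | 30.3% |
| 3 + 11 (20% and about 60%) | 14/33 = 42.4% | 20.0% | 9.1% | 42.4% |

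Total % here counts withdrawn patients as missing in the denominator, following SAP Section 3. With similar use in both groups the valid % hardly moves. With a large gap it falls and returns although nobody changed.

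**4. Effect on within-patient measures.** Under the same no-change assumption, reduction of at least 50% is 0% at every visit. A cross-tabulation of patients with both records gives 3/15 at start against 3/15 at visits 13 and 15, so no false change. For these measures the problem is narrower: the group at visits 13 and 15 is selected, and visit 16 mixes lengths of follow-up.

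**The case against.** The strongest reply is that the protocol endpoint is a within-patient change, and SAP 10.5 computes it from start of treatment to each visit. Step 4 shows that attendance alone cannot create a reduction in that measure. The planned contingency tables show no false change either if they cross-tabulate the same patients. This stands. The distortion reaches only the current-use percentages and an unpaired comparison of counts, and the SAP wording does not say which kind of table it means.

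A reader might infer that late results are bound to show a fall and then a rebound, and are merely artefacts. The documents do not support that. It needs a difference in growth-factor use between responders and non-responders that neither document gives.

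Two other absolute readings also go too far.

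- Visits 13 and 15 need not contain responders only: a loss of response first detected at week 24 or 36 is recorded at that visit.
- Not every withdrawn patient need have a visit 16: the protocol says they should return, and Section 7.2.3 provides for refusal and loss to follow-up.

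It can also be said that SAP 10.5 never calls visit 16 week 40, that reporting N with total and valid percentages exposes the drop in attendance, and that the study tests no formal hypothesis (Protocol 10.4.2) and plans no power for secondary variables (10.8). These points limit the stakes. They do not separate the two groups at visit 16, and seeing a lower N does not correct a pooled percentage.

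**Conclusion.** The point holds as one of time-point definition and denominators. SAP 10.5 sets visit 16 beside fixed-week visits, although the protocol makes it two visits under one number. For a patient withdrawn at week 16 it falls about 140 days before its nominal day. The early share of visit-16 records is about 55% at the protocol's assumed response, and 27% to 70% for 24 down to 10 responders. These shares assume that non-responders take their last dose at week 16, that nobody else leaves and that everyone attends.

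Current-use percentages at visits 13, 15 and 16, and any unpaired comparison of them with start of treatment, depend partly on who attends. The size of that effect cannot be derived from the documents. The within-patient reduction measure shows no false change, but it describes a selected group at visits 13 and 15 and mixed follow-up at visit 16. This should be corrected before analysis. It does not touch the primary endpoint.

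**What to change.** In SAP 10.5:

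1. Report visit 16 separately for patients who completed week 36 (week 40) and for early withdrawals, or place each early-withdrawal visit at its actual study week.
2. Calculate discontinuation or reduction of at least 50% among patients on that growth factor at start of treatment. Compare each visit with start of treatment within the same patients.
3. Label visits 13 and 15 as patients still on study, with their numbers.

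Week 16 (visit 11) may be highlighted as the latest visit before response-based withdrawal. This is an option rather than a correction, since the protocol names no main time point for the endpoint. A further split of week 40 by eltrombopag use after week 36 is not advised: no data item for it is specified, and the cells would be tiny.

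The cost is SAP wording and table shells. Visit dates, supportive-care records and end-of-study status are already collected. The downside is smaller denominators at week 40. In the illustration, at most the 3 responders on G-CSF at baseline would remain, so counts should be shown beside any percentage.
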